9.3 Primary Efficacy Endpoint(s) and Analyses

9.3.1 Primary Efficacy Endpoint

The primary endpoint is the proportion of subjects gaining 3 lines or more in mesopic, high-contrast, binocular DCNVA with no more than 5-letter loss in mesopic CDVA with the same refractive correction at Day 14, Hour 9 (3 hours after the second dose).

9.3.2 Main Analysis of Primary Efficacy Endpoint

The attributes of the estimand corresponding to the primary efficacy endpoint are summarized in Table 1.

Table 1. Summary of the Estimand Attributes of the Primary Efficacy Endpoint

Estimand Label	Attributes of the Estimand				
	Treatment	Endpoint	Population	Handling of Intercurrent Events	Statistical Summary
Estimand for the primary endpoint	AGN-190584 or vehicle	The proportion of subjects gaining 3 lines or more in mesopic, high contrast, binocular DCNVA with no more than 5-letter loss in mesopic CDVA with the same refractive correction at Day 14, Hour 9 (3 hours after the second dose)	ITT	The composite strategy will be applied to handle the intercurrent events. Missing data will be regarded as a non-responder for the endpoint.	The difference and the corresponding 95% confidence interval in the proportion of subjects gaining 3 lines or more in mesopic, high-contrast, binocular DCNVA with no more than 5-letter loss in mesopic CDVA with the same refractive correction at Day 14, Hour 9 between AGN-190584 and vehicle.

DCNVA = distance-corrected near visual acuity; CDVA = corrected distance visual acuity; ITT = intent-to-treat

As presented in the estimand for the primary efficacy endpoint in Table 1, the composite strategy will be used to handle the intercurrent events. Subjects with intercurrent events prior to Day 14, Hour 9 will be considered as non-responders for the primary efficacy endpoint. Subjects who have missing data for the primary efficacy endpoint will be categorized as non-responders in the primary analysis.

The comparison of the proportions between AGN-190584 and vehicle will be made using the Pearson's chi-square test. The treatment difference will be provided with a 2-sided 95% CI using the normal approximation based on the pooled variance without continuity correction.

If the proportions of subjects with reported IEs are considered unbalanced between the treatment groups and are higher in the vehicle group than in the AGN-190584 group, the subjects with IEs will not be considered as nonresponders for the primary efficacy analysis.

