5 STUDY ACTIVITIES

5.1 Eligibility Criteria

Subjects must meet all of the following criteria in order to be included in the study. Anything other than a positive response to the questions below will result in exclusion from study participation.

Consent

- 1. Subjects must voluntarily sign and date an informed consent, approved by an independent ethics committee (IEC)/institutional review board (IRB), prior to the initiation of any screening or study-specific procedures.

Demographic and Laboratory Assessments

- 2. Adult male or female, 40 to 55 years of age inclusive at the time of the screening visit
- 3. Are willing and able to comply with procedures required in this protocol.

Disease/Condition Activity

- 4. Subject meets the following ocular conditions:
 - Subjective complaints of poor near vision that impact activities of daily living, as defined by at least a moderate impact (score ≥ 3) on at least 1 question on the NEI VFQ-25 Questions 5 to 7 in the main questionnaire or Near Vision Subscale, Questions A3 to A5 in the Appendix of Optional Additional Questions, at the screening visit
 - Best cycloplegic distance correction at screening in the range of spherical -4.00 D to +1.00 D inclusively and cylinder $\leq \pm 2.00$ D with photopic, high-contrast binocular CDVA of 20/25 or better at the screening and baseline visits

- Photopic, high-contrast binocular CDVA of 20/32 or better by habitual monofocal correction (either spectacles or contact lenses), or willing to wear new monofocal correction spectacles to achieve photopic, high-contrast CDVA of 20/32 or better during the study
- Mesopic, high-contrast binocular DCNVA of 20/40 (J3) to 20/100 (J10) at the screening and baseline visits
- Photopic, high-contrast, near visual acuity correctable to 20/40 (J3+) or better in each eye at the screening visit
- Mesopic pupil diameter < 8.0 mm in both eyes at the screening visit

✓ 5. Subject does not meet any of the following ocular conditions:

- Severe dry eye disease (defined as total corneal staining \geq grade 3 on the 5-point Oxford scale and an OSDI score of > 33) at the screening visit
- Corneal abnormalities (including keratoconus, corneal scar, Fuchs' endothelial dystrophy, guttata, or edema) in either eye that are likely to interfere with visual acuity
- Narrow iridocorneal angles (Shaffer grade ≤ 2 or lower on gonioscopy examination), history of angle-closure glaucoma, or previous iridotomy

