2.3 Treatment Assignment and Blinding

Subjects will be randomized in a 1:1 ratio to receive either AGN-190584 or vehicle dosed twice daily, in each eye, for 14 days.

Randomization will be further stratified by the following stratification factors:

- Age group: ≤ 50 years and > 50 years
- Baseline binocular mesopic DCNVA severity: 20/63 or better, and worse than 20/63; with a maximum of 50% enrolled subjects with baseline binocular mesopic DCNVA of 20/63 or better
- Iris color: brown and nonbrown
- Emmetropie status: emmetrope and nonemmetrope; with a maximum of 25% enrolled subjects with non-emmetrope. A subject will be considered as emmetrope if both eyes of the subject satisfy the 2 criteria based on best cycloplegic distance correction: 1) -0.5D to +0.75D in sphere, inclusively; and 2) ≤ 0.75D in Cylinder.

All AbbVie personnel with direct oversight of the conduct and management of the study (with the exception of the AbbVie Drug Supply Management Team), the investigator, study site personnel, and the subject will remain masked to each subject's treatment throughout the study. To maintain the masking, the AGN-190584 and vehicle containers provided for the study will be identical in appearance. The IRT will provide access to unmasking subject treatment information in the case of a medical emergency.

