2.4 Sample Size Determination

The sample size calculation was considered for the primary efficacy endpoint, proportion of subjects gaining 3 lines or more in mesopic, high-contrast, binocular DCNVA with no more than 5-letter loss in mesopic CDVA with the same refractive correction at Day 14, Hour 9 (3 hours after the second dose).

Assuming a responder rate of 25% in the AGN-190584 group and 7% in the vehicle group, and a 5% dropout rate, a sample size of 100 subjects per study treatment group will

provide greater than 90% power using chi-square testing at a 2-sided significance level of 5%.

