9.0 Efficacy Analyses

9.1 General Considerations

All efficacy analyses will be conducted for all efficacy endpoints in the ITT population at the end of the study and after the database has been locked. All tests will be 2-sided at an alpha level of 0.05. All confidence intervals (CIs) will be at least 2-sided 95% confidence.

Unless otherwise specified, the comparison of the proportions between AGN-190584 and vehicle will be made using the Pearson's chi-square test, and the treatment difference will be provided with a 2-sided 95% CI using the normal approximation based on the pooled variance without continuity correction.

Continuous variables will be analyzed using an analysis of covariance (ANCOVA) model that includes treatment, age group, baseline DCNVA severity group, iris color group, and emmetrope status as factors as well as corresponding baseline value as a covariate.

Unless otherwise specified, any mis-stratified subject will be analyzed based on the actual stratum the subject should have been randomized.

"Baseline" refers to the last non-missing observation before the first administration of study treatment or randomization if no study treatment is given. The change from baseline values will be computed as the postbaseline value minus the baseline value.

For descriptive analyses:

- Categorical variables will be summarized with the number and percentage of subjects; unless otherwise stated, percentages will be calculated based on the number of non-missing observations.
- Continuous variables will be summarized with descriptive statistics (number of nonmissing observations, mean and standard deviation, median, 1st and 3rd quartiles, minimum, and maximum).

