9.3.3 Sensitivity and Supplementary Analyses of the Primary Efficacy Endpoint

As a sensitivity analysis, a 2-sided 95% confidence interval using the Wilson-Newcombe method will be presented.

In addition, the following sensitivity analyses with respect to missing data handling approaches will be conducted to explore the robustness of the primary efficacy analysis results:

- Observed data without imputation: The comparison between AGN-190584 and vehicle for the primary efficacy endpoint will be made using the Pearson's chi-square test based on observed data without imputation.
- Last observation carried forward (LOCF): Missing data for the primary efficacy endpoint at Day 14, Hour 9 will be imputed using a time matched LOCF, and the comparison between AGN-190584 and Vehicle for the primary efficacy endpoint will be conducted based on the data after imputation.

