9.4.4 Supportive Secondary Efficacy Endpoints and Analyses

Supportive Secondary Endpoints:

1. Proportion of subjects gaining 2 lines or more in mesopic, high-contrast, binocular DCNVA with no more than 5-letter loss in mesopic CDVA with the same refractive correction at Day 14, Hour 9 (3 hours after the second dose)
2. Proportion of subjects achieving 20/40 or better in mesopic, high-contrast, binocular DCNVA with no more than 5-letter loss in mesopic CDVA with the same refractive correction at Day 14, Hour 9 (3 hours after the second dose)

The same analysis method as described in Section 9.3.2 for the primary efficacy endpoint will be applied for the above supportive secondary endpoints. The comparison of the proportions between AGN-190584 and vehicle will be made using the Pearson's chi-square test. The treatment difference will be provided with a 2-sided 95% CI using the normal approximation based on the pooled variance without continuity correction.

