9.5 Additional Efficacy Endpoints and Analyses

The additional efficacy endpoints are:

1. Change from baseline in mesopic Near Vision Presbyopia Task-based Questionnaire (NVPTQ) Performance score at Day 14, Hour 9 (3 hours after the second dose)
2. Change from baseline in Presbyopia Impact and Coping Questionnaire (PICQ) Coping score at Day 14, Hour 3
3. Change from baseline in Visual Function Assessment application (VFA app) at Day 14, Hour 9 (3 hours after the second dose):
 - Change from baseline in average number of blinks per minute
 - Change from baseline in median working distance (centimeters)
 - Change from baseline in median magnification level (%) from the original size

- Change from baseline in reading speed (words per minute)
- Change from baseline in median contrast level (%) based on the original value

The PRO scoring algorithms for the NVPTQ, PICQ, and VFA app are provided in Appendix A.

The additional efficacy endpoints will be analyzed using an ANCOVA model that includes treatment, age group, baseline DCNVA severity group, iris color group, and emmetrope status as factors as well as corresponding baseline PRO score as a covariate.

The same analysis will be applied for these PRO scores at other visits/timepoints.

Additionally, for the PRO domain mesopic NVPTQ Performance score at Day 14 Hour 9 and the PRO domain PICQ Coping score at Day 14 Hour 3, the cumulative distribution function (CDF) curves representing the cumulative proportion of subjects with any particular level of change from baseline in a PRO domain will be presented by treatment group.

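### The four confirmatory tests ignore the randomisation strata; a stratified test is a cheap gain, about 1 point of power or less for H1 and possibly several for H4

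*SAP*

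**What the plan says.** SAP 2.3 and Protocol 5.8 stratify the 1:1 randomisation by four binary factors, which makes 16 cells. One of them is "Baseline binocular mesopic DCNVA severity: 20/63 or better, and worse than 20/63", with the better group capped at 50% of enrolment.

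For the primary endpoint, SAP 9.3.2 and Protocol 7.4 state: "The comparison of the proportions between AGN-190584 and vehicle will be made using the Pearson's chi-square test". The accompanying interval for the difference is a normal approximation with pooled variance. SAP 9.4.2 repeats this for H2, and SAP 9.4.4 for H3 and H4.

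The sensitivity analyses in SAP 9.3.3 and 9.4.3 vary the interval method ("As a sensitivity analysis, a 2-sided 95% confidence interval using the Wilson-Newcombe method will be presented") and the handling of missing data. None is stratified or adjusted.

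The strata are used elsewhere. The additional continuous endpoints "will be analyzed using an ANCOVA model that includes treatment, age group, baseline DCNVA severity group, iris color group, and emmetrope status as factors" (SAP 9.5), and SAP 9.1 already rules that "any mis-stratified subject will be analyzed based on the actual stratum the subject should have been randomized". The factors otherwise appear only as descriptive subgroups (SAP 9.7).

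**The concern.** Stratified allocation balances the factors between arms. If a factor predicts response, this balance makes the observed difference less variable, but the unstratified test still uses the full pooled variance. The test is then conservative and its interval wider than it needs to be. The plan gets no benefit from its stratification in the only four tests under type I error control, although it adjusts for all four factors in the lower-ranked continuous endpoints.

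The documents give no prognostic strength for any factor, but for H4 a link follows from the definitions. H4 is the "Proportion of subjects achieving 20/40 or better in mesopic, high-contrast, binocular DCNVA", with the CDVA condition. Entry requires "Mesopic, high-contrast binocular DCNVA of 20/40 (J3) to 20/100 (J10) at the screening and baseline visits". The severity stratum is cut at 20/63. A subject who enters at 20/40 already meets the DCNVA part of H4, while a subject in the worse stratum has several lines to gain. What is at stake is power for the last step of the fixed sequence and, to a much smaller degree, precision for H1.

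**Working it through.** **1. The plan's own power.** Inputs from SAP 2.4: "Assuming a responder rate of 25% in the AGN-190584 group and 7% in the vehicle group", 100 per arm, 5% dropout, two-sided 5%. With p̄ = (p1 + p2)/2,

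power = Φ{ [(p1 − p2) − 1.96·√(2p̄(1 − p̄)/n)] / √([p1(1 − p1) + p2(1 − p2)]/n) }.

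- n = 95 per arm: (0.18 − 1.96 × 0.0532)/0.0516 = 1.47, power 92.9%.
- n = 100, no dropout: 94.1%.
- n = 100, dropouts as nonresponders (23.75% vs 6.65%): 92.6%.

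Exact enumeration gives 94.1%, 95.2% and 94.0% respectively. The stated figure of more than 90% reproduces.

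**2. H1, unstratified versus stratified.** Simulation: 200 subjects, permuted blocks of 4 in 16 strata, 20,000 trials per scenario (Monte Carlo SE about 0.15 point). Marginal rates are held at 25% and 7%. Block size, factor prevalences (50/50/50/25%) and log-odds ratios are assumptions. The Cochran-Mantel-Haenszel (CMH) test uses four cells, age group by DCNVA severity.

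| Prognosis assumed | Pearson | CMH | Pearson, 5% dropout | CMH, 5% dropout | Size at 16%/16%: Pearson / CMH |
|---|---|---|---|---|---|
| None | 95.4% | 95.2% | 93.7% | 93.5% | 5.3% / 5.2% |
| Log-OR 1 for age and DCNVA | 95.6% | 96.0% | 94.6% | 95.0% | 4.4% / 5.1% |
| Log-OR 1.4 for each, 0.5 for iris | 95.7% | 96.5% | 95.0% | 95.9% | 4.1% / 5.1% |

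A separate simulation over other odds ratios gave −0.3 to +0.3 point for severity odds ratios of 1 to 3, +0.5 to +0.9 at 5, and +0.9 to +1.3 only at 10.

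The Mantel-Haenszel difference with Sato variance has an interval 3.3%, 5.4% and 7.1% narrower in the three scenarios, with 94.7% to 94.9% coverage. About 3.3% of that comes from dropping the pooled variance. Stratifying itself therefore contributes about 0, 2.1 and 3.8 percentage points.

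**3. H4, the structural link.** On a chart with 0.1-logMAR steps (assumed), the lines needed to reach 20/40 are:

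| Baseline | 20/40 | 20/50 | 20/63 | 20/80 | 20/100 |
|---|---|---|---|---|---|
| Stratum | better | better | better | worse | worse |
| Lines needed | 0 | 1 | 2 | 3 | 4 |

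**4. H4, a hand check of the mechanism.** Take a normal letter-gain model calibrated so that 25% and 7% gain at least 15 letters. Assume SD 7 letters, half of subjects in each stratum, an equal mix of lines in the better stratum, a 60:40 mix of 20/80 and 20/100 in the worse, and dropouts as nonresponders. Response rates are 0.70 vs 0.46 (better), 0.17 vs 0.05 (worse) and 0.438 vs 0.253 overall, a difference of 0.185.

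- Variance used by Pearson: 0.3455 × 0.6545 = 0.226; SE = √(2 × 0.226/100) = 0.0672.
- Variance within strata: ½(0.58 × 0.42) + ½(0.11 × 0.89) = 0.171; SE = √(2 × 0.171/100) = 0.0584, about 13% smaller.
- Actual SD of the difference under stratified allocation: √{[½(0.70 × 0.30 + 0.17 × 0.83) + ½(0.46 × 0.54 + 0.05 × 0.95)]/100} = 0.0569.
- Pearson power: Φ[(0.185 − 1.96 × 0.0672)/0.0569] = Φ(0.94), about 82.5%. CMH: Φ[(0.185 − 1.96 × 0.0584)/0.0569] = Φ(1.24), about 89%.

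Simulation of the same model gave 83.2% and 89.9%.

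**5. H4, range.** A line-gain model calibrated to the same 25% and 7%, with SD 1.5 lines, even baseline lines and half of subjects in each stratum, gives rates of 44% vs 25%, power of 87.9% (Pearson) vs 93.5% (CMH), and size of 2.8% vs 4.9%. With 5% dropouts as nonresponders, power is 83.4% vs 90.0% and size 2.4% vs 4.9%.

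- If the better stratum gains 0.5, 1 or 1.5 lines less on average, the benefit falls to 2.9, 0.9 or 0.3 points.
- SD 2.0 lines: 0.7 to 2.4 points. SD 1.0 line: 7 to 22 points.

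All H4 runs ignore the CDVA condition. Power for H2 and H3 was not computed separately, because no rates are stated.

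**6. Effect through the fixed sequence.** Requiring H1, H3 and H4 all to reject (H2 not modelled), power in the SD 1.5 model is 80.1% vs 85.5%.

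**7. Downside.** If no factor is prognostic, the four-cell CMH test costs about 0.2 point for H1 and 0.3 point for H4 (81.4% vs 81.1% at 44% vs 25%). A 16-cell CMH test can cost up to 1.6 points for H4. Stratifying by severity alone performed the same as four cells in the SD 1.5 model (93.4% vs 93.3%).

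**The case against.** The planned test is valid. Protocol and SAP agree on it, the sample size was planned on it, and for H1 about 1 point on roughly 95% power is a design preference. All of that stands, and it is why this is not called an error.

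The H4 benefit rests on assumed rates, gain SD and baseline mix, and shrinks when better-baseline subjects gain fewer lines. H4 is also a supportive endpoint, tested last. With H1, H3 and H4 all required to reject, a separate run at SD 1.5 lines gave gains of 5.3 points with equal line gains and 2.5, 1.4 and 0.8 points if the better stratum gains 0.5, 1 or 1.5 lines less. At SD 2.0 the gains were 0.5 to 2.2 points (SE about 0.5). So the size is uncertain, but the estimated gain was positive in every line-gain scenario.

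Changing Protocol 7.4 is an amendment that needs IEC/IRB approval (Protocol 8.1). That cost is real but modest. A stratified sensitivity analysis in the SAP alone would avoid it, but would not change the confirmatory tests.

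Operations Manual 6.5 refers to a 1-hour DCNVA when the stratum is confirmed, although randomisation is at Hour 0. For the analysis, SAP 9.1 settles this: baseline is the last value before the first dose, and the actual stratum is used.

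Finally, the documents do not show that age is prognostic. Including it costs little, and severity carries nearly all of the H4 gain.

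**Conclusion.** The point holds as a matter of efficiency. All four confirmatory tests discard the stratification. For H1 the loss is under 1 point for severity odds ratios up to 5, at most about 1.3 points at an extreme odds ratio of 10, and slightly negative if nothing is prognostic. For H4 the direction follows from the trial's own definitions, unless worse-baseline subjects gain many more lines. The size depends on the assumed gain distribution: about 5 to 7 points in the central models, 0.3 to 22 points across all those run, and realised only if H1 to H3 succeed. Validity of the primary conclusion is not in question.

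**What to change.** Before unmasking, revise SAP 9.1, 9.3.2, 9.4.2 and 9.4.4 and Protocol 7.4 as follows.

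- Main test of H1 to H4: Cochran-Mantel-Haenszel, stratified by age group × baseline mesopic DCNVA severity (four cells), using actual strata under the existing SAP 9.1 rule and its pre-dose baseline.
- Estimate: Mantel-Haenszel risk difference with Sato variance and 95% interval.
- Sparse-cell rule: if any of the four cells holds fewer than 10 subjects in total, checked while masked, stratify by DCNVA severity alone.
- Move the unstratified Pearson test and its pooled-variance interval to SAP 9.3.3 and 9.4.3 as a sensitivity analysis.

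This needs SAP wording, a few lines of code and a protocol amendment with IEC/IRB review; no extra subjects or data. It has to be prespecified, because a stratified test chosen after unmasking would be post hoc.

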8.0 Handling of Potential Intercurrent Events for the Primary and Key Secondary Endpoints

The primary efficacy endpoint (defined in Section 3.1) and the key secondary efficacy endpoint (defined in Section 3.2) will be analyzed based on the ITT population and the following methods will be used to address potential intercurrent events (IE):

- Subjects who prematurely discontinued study treatment before the Day 14 visit will be considered as nonresponders.

- Subjects who die before assessment of the endpoint will be considered as nonresponders for the endpoint.
- Subjects who are lost to follow-up and are missing data for the endpoint will be considered as non-responders for the endpoint.

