9.2 Handling of Missing Data

Unless otherwise specified, for the main analyses of primary and secondary efficacy endpoints and the other efficacy endpoints based on the binary data, subjects with missing data will be regarded as nonresponders. Other efficacy endpoints will be analyzed as observed.

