9.4.2 Main Analyses of Key Secondary Efficacy Endpoint

The attributes of the estimand corresponding to the key secondary efficacy endpoint are summarized in Table 2.

Table 2. Summary of the Estimand Attributes of the Key Secondary Efficacy Endpoint

Estimand Label	Attributes of the Estimand				
	Treatment	Endpoint	Population	Handling of Intercurrent Events	Statistical Summary
Estimand for the key secondary endpoint	AGN-190584 or vehicle	The proportion of subjects gaining 3 lines or more in photopic, high-contrast, binocular DCNVA with no more than 5-letter loss in photopic CDVA with the same refractive correction at Day 14, Hour 9 (3 hours after the second dose)	ITT	The composite strategy will be applied to handle the intercurrent events. Missing data will be regarded as a non-responder for the endpoint.	The difference and the corresponding 95% confidence interval in the proportion of subjects gaining 3 lines or more in photopic, high-contrast, binocular DCNVA with no more than 5-letter loss in photopic CDVA with the same refractive correction at Day 14, Hour 9 between AGN-190584 and vehicle.

DCNVA = distance-corrected near visual acuity; CDVA = corrected distance visual acuity; ITT = intent to treat

As presented in the estimand for the key secondary efficacy endpoint in Table 2, the composite strategy will be used to handle the intercurrent events. Subjects with intercurrent events prior to Day 14, Hour 9 will be considered as non-responders for the key secondary efficacy endpoint. Subjects who have missing data for the key secondary efficacy endpoint will be categorized as non-responders in the primary analysis.

The comparison of the proportions between AGN-190584 and vehicle will be made using the Pearson's chi-square test. The treatment difference will be provided with a 2-sided 95% CI using the normal approximation based on the pooled variance without continuity correction.

If the proportions of subjects with reported IEs are considered unbalanced between the treatment groups and are higher in the vehicle group than in the AGN-190584 group, the subjects with IEs will not be considered as nonresponders for the key secondary efficacy analysis.

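### The nonresponder rule for the primary and key secondary endpoints is withdrawn on an undefined judgement of imbalance, so the main analysis is not fixed in advance

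*SAP*

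**What the plan says.** Protocol Table 2 sets a composite strategy for the primary and key secondary endpoints. Protocol Sections 7.3 and 7.4 make subjects with IEs before Day 14 Hour 9 nonresponders, with no condition attached.

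SAP Section 8.0 repeats the rule for both endpoints: "Subjects who prematurely discontinued study treatment before the Day 14 visit will be considered as nonresponders". It also lists a missing-data case as an IE: "Subjects who are lost to follow-up and are missing data for the endpoint will be considered as non-responders for the endpoint". SAP Tables 1 and 2 again name the composite strategy.

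The last sentence of SAP Section 9.3.2 makes an exception. Its trigger, which compares IE proportions by arm, reads: "subjects with reported IEs are considered unbalanced between the treatment groups and are higher in the vehicle group than in the AGN-190584 group". Its consequence is that "the subjects with IEs will not be considered as nonresponders for the primary efficacy analysis". Section 9.4.2 ends the same way: "the subjects with IEs will not be considered as nonresponders for the key secondary efficacy analysis".

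The missing-data rule is left in place. Section 9.2 says that "subjects with missing data will be regarded as nonresponders", and Section 9.3.2 says "Subjects who have missing data for the primary efficacy endpoint will be categorized as non-responders in the primary analysis".

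On timing, Section 9.1 says only that efficacy analyses are "conducted for all efficacy endpoints in the ITT population at the end of the study and after the database has been locked". Section 12.1 marks a data monitoring committee as not applicable. Section 9.4.4 adopts the 9.3.2 method for the supportive endpoints H3 and H4 but does not repeat the exception.

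**The concern.** The exception concerns the main analysis of H1, which gates H2 to H4 in the fixed sequence, and the main analysis of H2. Four things needed to apply it are absent from both documents:

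- the size of imbalance that counts;
- who decides;
- when the decision is made;
- how the affected subjects are then analysed.

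Whether IEs are higher on vehicle cannot be judged without data that identify the arms, and the only timing given for the efficacy analyses is after database lock.

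The exception also conflicts with the protocol estimand, SAP Section 8.0 and SAP Table 1. For subjects lost to follow-up with missing data it conflicts with the missing-data rule: one sentence says they are not nonresponders and another says they are. Two competent statisticians could follow the SAP and report different primary p-values.

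**Working it through.** **Inputs from the documents.** 100 per arm, 25% versus 7%, 5% dropout not split by arm (Protocol 7.8, SAP 2.4); Pearson chi-square without continuity correction, 2-sided 0.05 (SAP 9.1, 9.3.2).

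**The plan's own figure.** Counting 5% in each arm as nonresponders gives 0.95 × 25% = 23.75% and 0.95 × 7% = 6.65%, mean 15.2%.

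- Null SE = √(2 × 0.152 × 0.848 / 100) = 0.0508.
- Alternative SE = √((0.2375 × 0.7625 + 0.0665 × 0.9335) / 100) = 0.0493.
- Power = Φ((0.171 − 1.96 × 0.0508) / 0.0493) = 92.6% (exact enumeration 94.0%).

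The stated power above 90% is reproduced under the unconditional rule.

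**Reading of the exception.** The most natural reading is: use the observed Day 14 Hour 9 value if there is one, otherwise nonresponse, because the ITT population and the missing-data rule remain. The exception then affects only subjects who stopped study drug but still have Hour 9 data. Let f be the share of IE subjects with such data.

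**Assumptions.** IE rates by arm and f are not in the documents and are varied. IE subjects respond at their arm's rate. Two possible meanings of unbalanced are compared: any vehicle excess, and a vehicle excess with p<0.05. The first leaves no separate role for the word unbalanced, so it is an upper bound.

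**How often the exception fires:**

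| IEs, active/vehicle | Any excess | p<0.05 |
|---|---|---|
| 5%/5% | 43% | 2% |
| 2%/8% | 97% | 49% |
| 6%/3% | 11% | 0.1% |

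**How often the H1 decision differs from the fixed rule at 25% versus 7%** (1,000,000 simulated trials per scenario):

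| IEs | Any excess: f=0 | f=0.25 | f=0.5 | f=1 | p<0.05: f=0.25 | f=1 |
|---|---|---|---|---|---|---|
| 5%/5% | 0% | 0.27% | 0.47% | 0.75% | 0.01% | 0.04% |
| 2%/8% | 0% | 0.47% | 0.87% | 1.55% | 0.22% | 0.82% |
| 6%/3% | 0% | 0.06% | 0.11% | 0.17% | 0.00% | 0.00% |

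**Disagreement between two analysts who differ only in the trigger.** At plan, with IEs 5%/5% or 2%/8%, they reach different H1 decisions in 0.3% (f=0.25) to 0.7% (f=1) of trials. At 20% versus 10% with IEs 2%/8%, where power is about 57%, they differ in 1.1% to 3.1%.

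**Borderline example**, using z = (difference in proportions) / √(p̄(1 − p̄) × 2/100), where p̄ is the pooled proportion:

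- IEs 2 versus 8: p̄ = 0.05, z = 0.06/0.0308 = 1.95, p=0.052. A p<0.05 trigger does not fire; an any-excess trigger does.
- IEs as nonresponders, 19 versus 9: p̄ = 0.14, z = 0.10/0.0491 = 2.04, p=0.042. H1 passes.
- One vehicle IE subject an observed responder and neither active IE subject one, 19 versus 10: p̄ = 0.145, z = 0.09/0.0498 = 1.81, p=0.071. H1 fails.
- IE subjects excluded instead, 19/98 versus 9/92: p=0.062. H1 fails.

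**Near the planned effect.** 24 versus 7 gives p=0.0009. If six vehicle IE subjects are observed responders, 24 versus 13 still gives p=0.045.

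**The case against.** The exception is one-directional and guards against bias in favour of the drug: IEs counted as failures mainly on vehicle would flatter AGN-190584. That is correct. With equal true response of 7% to 15% and assumed IEs of 2%/10%, the one-sided error in favour of the drug (nominal 0.025) is 0.034 to 0.044 under the fixed rule. With the switch at any vehicle excess it is 0.024 to 0.026 if all IE subjects have Hour 9 data. Deletion therefore gives up some protection. If only a quarter have data, however, the switched error is 0.032 to 0.038, so the protection may be small.

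The affected group may also be nearly empty. The endpoint is timed from the second visit-day dose, Protocol Section 5.6 keeps stopped subjects in the study for safety assessments, and near acuity is not among the safety measures. This points to a low f; at f=0, on the reading used here, nothing changes.

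The borderline example is a chosen one. If one active IE subject were also an observed responder, 20 versus 10 gives p=0.048 and H1 passes.

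Finally, the observed-data and LOCF sensitivity analyses are already planned whatever the IE balance.

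These points limit the size of the problem. They do not supply a trigger or a handling rule, and they do not remove the contradiction with the protocol, SAP Section 8.0 and SAP Tables 1 and 2.

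**Conclusion.** The concern holds and should be fixed. The SAP contradicts itself and the protocol on the gating analysis and leaves the choice to an undefined judgement that requires arm-level data. The defect is in pre-specification; it is not a rule that inflates type I error, and the stated power is unaffected.

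The practical effect near the planned effect is small, and the conclusion is at risk mainly in borderline results. These sizes rest on assumed IE rates by arm, an assumed share of IE subjects with Hour 9 data, and the observed-value reading of the exception. Whether the exception reaches H3 and H4 through Section 9.4.4 is arguable.

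**What to change.** Before unmasking:

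1. Delete the conditional sentence from SAP Sections 9.3.2 and 9.4.2, so that the composite nonresponder rule is the unconditional main analysis for H1 and H2.
2. State in Section 9.4.4 that the same rule applies to H3 and H4. The protocol gives the rule only for H1 and H2 and leaves the supportive endpoints to the SAP.
3. Add to Sections 9.3.3 and 9.4.3 one supplementary analysis that uses the observed Day 14 Hour 9 value regardless of IE and is reported whatever the balance. Give it a missing-value rule that also covers subjects without Day 7 data, for example multiple imputation within arm from baseline DCNVA severity and Day 7 Hour 9 response, with an absent Day 7 value imputed in the same step.
4. State whether the existing observed-data analysis uses the observed values of IE subjects.

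If the sponsor wants the safeguard in the main analysis, the alternative is to fix a numeric trigger and one handling rule before unmasking, and to reconcile SAP Section 8.0, SAP Tables 1 and 2 and Protocol Sections 7.3 and 7.4 with it.

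**Cost.** The first route is SAP text and one extra analysis per endpoint; the alternative also needs protocol text. Sample size is unchanged. The downside of deletion is that the main analysis no longer adjusts for excess vehicle IEs. In the equal-response scenarios above, the supplementary analysis has one-sided error of about 0.026 to 0.028 (simulated with imputation from the arm's response rate, without covariates). It makes any gap visible but does not decide H1.
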